The clinician dashboard is also produced by BrightInsight, Inc to work in conjunction with the DMP App for patients. AstraZeneca aims to strengthen existing clinical resources and reduce the burden and time spent on patient preparation and follow-ups by surfacing real-time insights to clinical teams and providing the tools to support patients easily and efficiently. The dashboard features secure, 2-way messaging to individuals and groups of patients, enabling efficient follow-up to answer patients’ questions and outreach to encourage engagement with the disease management platform. Clinicians can also reach out to patients through multi-channel communication methods, including email linked to Patient Gateway and a text chat feature in the App, to promote engagement and responses to surveys. The clinical team is alerted based on patients’ survey responses and engagement patterns, allowing them to identify risks, intervene early through supportive messaging, and reduce post-admission recovery complications. In summary the goals here is to provide, the real-time information about patients’ health status, combined with secure easy messaging with patients, which will enable an efficient, effective workflow for clinical teams to support patients through recovery and health maintenance.

III. RESEARCH DESIGN AND METHODS

Sample size: 70 post hospital admission at Massachusetts General Hospital (MGH), general cardiology with a diagnosis of heart failure with reduced ejection fraction (HFrEF), heart failure with moderate ejection fraction (HFmEF), or heart failure with preserved ejection fraction (HFpEF). Patients will be identified via an automated computer-based algorithm using information retrieved from electronic health records {Protocol #: 2020P002432}.

Inclusion/Exclusion Criteria for intervention study population

- **Intervention study population:** Patients 21 years and older with a diagnosis of heart failure [HFrEF(<40%), HFmEF(40-49%) HFpEF(≥50%)] admitted to MGH cardiology services (Ellison 10 and 11). Patients must have access to smartphone and email, be English speaking/reading and discharged home.

Non-recruited EHR-based control populations for the exploratory objectives for this single-arm interventional pilot:

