 - a. Heart failure symptoms will be measured as the changes in KCCQ scores between the 30 day and 60 day time-points.
2. Patient daily log compliance.
 - a. Daily log compliance will be measured after 60 days using the total number of days patient completes daily log in the AMAZE™ app out of total days patient is enrolled in the app.
3. Patient app usage.
 - a. Patient app usage will be measured as the number of days the patient engages (i.e. completes daily log, sends a message) with the app at least once a day during the study period.
4. Patient app messaging.
 - a. Patient app messaging will be measured as the number of messages sent by the patient during the 60 day study period.
5. Changes in hospital readmissions.
 - a. Hospital readmission rates in the enrolled study group will be compared to readmission rates in historical control groups.
6. Use of ancillary healthcare resources.
 - a. Rates ancillary healthcare resources (i.e. emergency room visits, urgent care visits, unexpected ambulatory care visits, cardiac rehab) in the enrolled study group will be compared to rates of usage in a historical control group.

Subject Enrollment

Overview

Approximately 70 patients will be enrolled in the study. Patients admitted to MGH cardiology will be screened by study staff for inclusion/exclusion criteria. Study staff will obtain approval to approach eligible patients by the inpatient clinical team. Approximately 2-days prior to discharge, suitable patients will be consented and onboarded with study staff, with the technical support available 24/7 via email or phone through BrightInsight, Inc.

Procedure for obtaining informed consent

We will use Mass General Brigham electronic resources to identify and screen patients for the eligibility criteria listed above. Our internal (MGH) data and analytics team developed an automated process to screen and extract a list of eligible admitted patients on Ellison 10/11 through Research Patient Data Registry (RDPR) and Enterprise Data Warehouse (EDW) (IRB Protocol # 2020P002432). The list will be sent to the study staff daily; study staff will perform chart review of participants on the list to confirm eligibility.

We will focus on patients with a diagnosis of heart failure, who speak and read English.

We will also use the attached study flyer to advertise the study to patients on inpatient floors, with nurse manager approval for the respective floors.

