Patients will be surveyed for baseline demographics and study outcomes. Medical history, including labs, procedures, and diagnoses will be collected from the medical record and recorded in REDCap

At consent, subjects will be surveyed for demographics that cannot be obtained from the medical record (See “Baseline Demographics” attachment).

Quality of life will be collected through the patient-facing AMAZE app (See “KCCQ” attachment). Patient satisfaction will be collected through MAUQ (attached) administered through the app. The app will also track patient medication adherence, and facilitate symptom, blood pressure, weight, and activity tracking.

At roughly 30 days from enrollment and again at 60 days from enrollment, a research coordinator will call the patient to collect 1) current cardiac medications and any changes to medication regimen and 2) hospitalizations, ED presentations, urgent care visits, primary care or cardiology visits, and cardiac rehab enrollment at institutions outside MGB. Research coordinators will review subject medical records to determine these events at MGB.

EHR data for the control populations (MGH and BWH) will be obtained from RPDR. We may also review medical records for these patients to collect/confirm EHR data.

Optional interviews

Two rounds of interviews regarding the user experience of the AMAZE app may be conducted over the course of the study. The interview questions ask about usability and helpfulness of the app, along with the option to give feedback about technical issues and features that could use improvement. These interviews

are optional and do not affect the participants' overall participation in the study. This is reflected in the consent form, with a section allocated to participants' choice of whether they would like to be contacted for these interviews or not.

Participants who consent to being contacted for the interviews will be selected based on engagement with the app. We will measure engagement by percentage of daily log compliance over the past seven days. Participants who fill out the daily log more than half the days in a week will be classified as "engaged with the app" and those who fill out the daily log less than half the days in a week will be categorized as "disengaged with the app."

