A Vendor Information Security Plan (VISP) (see “VISP_BrightInsight_Modular Final” attachment) was completed to evaluate the capacity of BrightInsight, Inc. to protect personally identifiable research data and other confidential information. In summary, BrightInsight is committed to the security and privacy of the platform and the digital solutions being built on top of the platform, whereby minimizing the risk for Astra Zeneca and Partners Health Care. To meet that end, BrightInsight has the following security and privacy certifications:

- HIPAA Compliant
- HITRUST CSF v9.1
- HITRUST Certification of the NIST Cybersecurity Framework
- ISO / IEC 27001: 2013
- EU-Swiss Privacy Shield
- Swiss-EU Privacy Shield
- GDPR Compliant
- French HDS Certification (*waiting for certificate*)

For medical appropriateness, a message does appear within the app consistent with other messaging tools instructing patients not to use the messaging system for medical emergencies. See language used below.

DISCLAIMER: Messages are not for medical emergencies. For medical emergencies call 911 immediately.

IV. PRIVACY AND CONFIDENTIALITY

Study Data

MGH

Screening and enrollment logs will be kept in the study e-regulatory binder in MGB Dropbox for Business. Study subject data will be kept in a password protected database (REDCap); subject records will be linked to unique subject IDs. Only study personnel who have undergone the proper human research training will have access to these data. Computers that will be used to access and analyze the data the data include MGB build computers, MGB Purchased Laptops, or study staff Personal Laptops encrypted to MGB standards.

Data for BWH controls will be obtained through RPDR/chart review, and stored in the study e-regulatory binder in Partners Enterprise Dropbox.

Data collected through the patient facing app that is sent to the sponsor (described below) will also be sent to MGH by BrightInsight to research staff via MGB secure file transfer

<https://rc.partners.org/kb/article/2729>.

Sponsor

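### Exploratory outcomes 5a and 6a compare groups whose events are found in different ways, and neither says which event source counts

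*Combined protocol and SAP*

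**What the plan says.** Section III, Study Outcomes, describes the readmission comparison in one sentence: "Hospital readmission rates in the enrolled study group will be compared to readmission rates in historical control groups". Outcome 6a has the same form for emergency, urgent, ambulatory and rehabilitation care. Neither names an event source.

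The sources appear under Data Collection and Surveys, and they differ by group.

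- **Enrolled, outside MGB.** "At roughly 30 days from enrollment and again at 60 days from enrollment, a research coordinator will call the patient" and, among other things, ask about "hospitalizations, ED presentations, urgent care visits, primary care or cardiology visits, and cardiac rehab enrollment at institutions outside MGB".
- **Enrolled, inside MGB.** "Research coordinators will review subject medical records to determine these events at MGB".
- **Controls.** "EHR data for the control populations (MGH and BWH) will be obtained from RPDR", followed by "We may also review medical records for these patients to collect/confirm EHR data". Section IV, Study Data, is firmer for one site: "Data for BWH controls will be obtained through RPDR/chart review".

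Section III introduces the controls as "Non-recruited EHR-based control populations for the exploratory objectives for this single-arm interventional pilot". No contact with them is described anywhere.

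**The concern.** A rate comparison is like for like only if an event of a given kind has the same chance of being counted in each group. Here an admission to a hospital outside MGB can reach the enrolled data through a telephone call. For a control it can be found only if it happens to be noted in an MGB record.

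Data Collection and Surveys says that patients are surveyed for study outcomes and then lists the outside events, so the natural way to run 5a and 6a is to count everything known about each enrolled patient. Done that way, the enrolled rate has wider capture than the control rate. If the calls find more outside care than the charts do, the error runs against the platform: it can hide a reduction in readmissions but does not manufacture one. Readmissions and ancillary care belong to Specific Aim 2, and section II presents this pilot as a step towards a multi-center efficacy study, so the direction of these contrasts may be read with interest.

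**Working it through.** The plan gives no figure for 5a or 6a to reproduce, so this is an illustration.

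**Inputs from the plan.** About 70 enrolled patients; controls matched 1:2, so 2 × 70 = 140 per control population.

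**Assumed inputs.**
- f, the share of patients with an event whose events are all outside MGB: 10% to 30%.
- c, the share of those patients found by the calls.
- e, the share of those patients found in control charts.
- p, the 60-day risk of an event: 25%.
- No true effect, and the same f in both groups.

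**Pooling telephone-reported events.** Ratio = (1 − f + fc) / (1 − f + fe).

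| Capture, c vs e | f = 10% | f = 20% | f = 30% |
|---|---|---|---|
| 100% vs 0% (worst case) | 1/0.90 = 1.11 | 1/0.80 = 1.25 | 1/0.70 = 1.43 |
| 70% vs 0% | 0.97/0.90 = 1.08 | 0.94/0.80 = 1.18 | 0.91/0.70 = 1.30 |
| 70% vs 50% | 0.97/0.95 = 1.02 | 0.94/0.90 = 1.04 | 0.91/0.85 = 1.07 |
| equal | 1.00 | 1.00 | 1.00 |
| 50% vs 70% | 0.95/0.97 = 0.98 | 0.90/0.94 = 0.96 | 0.85/0.91 = 0.93 |

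The inclusion criteria require an established or planned primary cardiologist at MGH (at BWH for BWH controls), which may keep f low. At f = 5% the worst case is 1/0.95 = 1.05.

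**Masking.** In the worst case a true ratio of 0.80 would be seen as 0.80/0.90 = 0.89, 0.80/0.80 = 1.00 or 0.80/0.70 = 1.14.

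**Against random error.** The worst-case difference is p × f = 2.5, 5.0 or 7.5 points, that is 1.75, 3.5 or 5.25 of 70 patients. Ignoring the matching, the 95% half-width is 1.96 × √[0.25 × 0.75 × (1/70 + 1/140)] = 12.4 points. The bias is therefore 2.5/12.4 = 20% to 7.5/12.4 = 60% of the half-width.

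**MGB records only.** Ratio = (1 − f enrolled) / (1 − f control). It is 1.00 if the shares are equal. The next table lets them differ by 10 points and puts pooling on the same inputs.

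| f enrolled / f control | MGB only | Pooled, 70% vs 50% | Pooled, 100% vs 0% |
|---|---|---|---|
| 10% / 20% | 0.90/0.80 = 1.13 | 0.97/0.90 = 1.08 | 1/0.80 = 1.25 |
| 20% / 10% | 0.80/0.90 = 0.89 | 0.94/0.95 = 0.99 | 1/0.90 = 1.11 |
| 20% / 30% | 0.80/0.70 = 1.14 | 0.94/0.85 = 1.11 | 1/0.70 = 1.43 |
| 30% / 20% | 0.70/0.80 = 0.88 | 0.91/0.90 = 1.01 | 1/0.80 = 1.25 |

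With moderate capture, pooling lies nearer to 1 in all four rows. In the worst capture case, MGB-only lies nearer in three rows and about equally far in the fourth.

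**The case against.** The strongest reply is that the harm is conditional and small. Nothing in the plan says that telephone-reported events will be pooled. Outside and MGB events are collected by separate routes, so an MGB-only comparison remains possible at analysis and no data are lost. The controls serve exploratory objectives, no test or decision rule is attached to 5a or 6a, and even the worst-case bias is smaller than the sampling error. All of this stands, and it limits the severity. It does not remove the point, because the natural way to run these outcomes still sets wider capture against narrower.

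A second reply is that MGB-only counting is itself an assumption. That also stands: the second table shows that neither method wins throughout. The nurse navigator's link to the MGH team could draw enrolled care towards MGB; a 10% versus 20% outside share would make the enrolled rate look higher (1.13). This is why the pooled rate belongs beside the main result.

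Three stronger readings are tempting and are not supported.

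- **That the plan commits to a biased comparison.** It is silent on pooling, and it gives neither the outside share nor the capture rates, so size and net direction are unknown. Other differences, such as volunteer selection and smartphone ownership not being required of controls, may act the other way.
- **That no follow-up window exists.** Outcomes 5a and 6a do not repeat one, but 60 days appears in outcomes 2a and 4a, the call schedule, Clinician Surveying and section VI. The study schematic is not shown and may say more.
- **That timing cannot matter.** Enrollment may fall about 2 days before discharge or up to about 3 days after it, so 60 days from enrollment ends 58 to 63 days after discharge. At a constant hazard of −ln(0.75)/60 = 0.00479 per day, those windows give risks of 24.3% and 26.1%, or ratios of 0.97 and 1.04 to 25%. That covers start-date shifts only. A 60-day against a 30-day window would give 25%/13.4% = 1.87, although nothing indicates that such a mismatch is planned.

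**Conclusion.** The concern holds in a limited form. Events are ascertained differently in enrolled patients and controls, and 5a and 6a have no rule that puts the groups on one source. Confidence in that is high.

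The size is uncertain. Counting telephone-reported events for enrolled patients only gives a ratio of 1.11 to 1.43 with no true effect at the extreme of complete capture by calls and none in control charts. It gives 1.02 to 1.07 when capture is 70% versus 50%, and nothing when capture is equal. The 10% to 30% outside shares, the capture rates and the 25% risk are all assumptions. The patient-level model treats any event as a single outcome, so it does not size the separate components of 6a.

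This is a minor-to-moderate point about how exploratory contrasts may be read. The primary outcomes, conversion rate and MAUQ score, do not depend on it.

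**What to change.** State in 5a and 6a that the main between-group comparison uses events in MGB records only, extracted by the same registry and chart-review rule in all groups, over the same 60 days from index discharge. Report telephone-reported outside events separately and descriptively for enrolled patients. Give the rate that pools them as a sensitivity analysis, labelled as having wider capture in the enrolled group.

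State the limitations too: MGB-only counting understates total use, and it assumes a similar outside-MGB share in all groups. A 10-point difference in that share gives a ratio of 0.88 to 1.14 with no true effect, so the method is not less biased in every scenario. Its merit is a single source available for every group and a rule fixed before the data are seen.

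The cost is protocol wording and one extraction rule, with chart review applied equally to controls and enrolled patients. No new patient contact is needed.
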